## Methods

### *NET Device description*

Stimulation characteristics. The NET Device delivers alternating current via surface electrodes placed transcranially (bilaterally) on the mastoid processes (**Figure 1**). The device delivers multiple low-amperage waveforms at controlled frequencies and pulse widths that vary throughout each treatment day, with no net-direct current component; this approach differs from single-frequency, sinusoidal transcranial alternating current stimulation. Waveshapes were refined across several engineering iterations that adjusted for dynamic variations in skin impedance, electrode conductance, frequency and pulse-width related sensation, and orthogonal electrode pressure (e.g. from head pressure when sleeping), leading to improved rates of patient tolerability.

Stimulation is continuously available (except when bathing) for up to 7 days via transcutaneous electrodes of size approximately 1cm x 2cm. Stimulation output frequency varies from 4 to 3000 Hz and pulse width from 7 to 1024 microseconds. Stimulation output current varies from 0 to 3.2 mA (peak) into a 15 kOhm load, and output voltage varies from 0 to 44 volts (peak to peak).

Treatment is self-administered, and participants are instructed that they can control the device output intensity and duration according to perceived benefit.

Possible mechanisms of action. Earlier studies demonstrated that transcranial electrostimulation of the type delivered by the NET Device can attenuate the severity of opioid withdrawal [1–5]. Such neurostimulation is thought to modulate endogenous opioid, dopaminergic and serotonergic systems and the autonomic nervous system [40–42], which are dysregulated in the opioid-dependent state [6–12]. We hypothesize that self-titrated NET Device stimulation of these multiple interacting neurochemical systems may promote neuroplastic changes [13–16] that normalize functioning of these systems and support longer-lasting changes in drug-abstinence behavior. Although the mechanism of

action is not well-understood and is a subject for future investigation, treatment duration ( $\leq 7$  days, self-administered) is consistent with FDA-approved percutaneous nerve stimulators, and the outcome measurement period (up to 16 weeks from start of treatment) is consistent with results of open-label NET pilot studies in Kentucky and Scotland.

**Safety.** As a Non-Significant Risk device, FDA does not require submitting an Investigational Device Exemption for this study. Safety of the NET Device has not been established for persons who: (1) are pregnant, breastfeeding, or  $<18$  years old; (2) have serious heart conditions or a cardiac pacemaker; (3) have suffered a stroke, brain tumor, or brain injury; (4) have current epilepsy; (5) are suffering serious psychotic illness; or (6) are taking medications such as neurotransmitter blockers.

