**Table 2** presents study inclusion and exclusion criteria. For inclusion, participants ages 18-65 years old must have current OUD, present in otherwise good health, be seeking opioid discontinuation at the treatment facility, self-report that they wish to become/remain abstinent without using MOUD, be willing to follow study procedures, provide informed consent and use medically-accepted highly effective contraception. An additional criterion (following informed consent) is that device use will not begin until the Clinical Opiate Withdrawal Scale (COWS [17]) total score is 13 or greater (at least moderate withdrawal); thus, a consented participant could be dis-enrolled if the latter criterion is not met. Exclusion criteria include pregnancy or lactation, serious current psychiatric disorder (schizophrenia, bipolar) or use of neuropsychiatric medications that may overlap with NET's proposed mechanisms of action (e.g. anxiolytics, antidepressants, anticonvulsants, sedating H1-receptor antihistamines, prescription or over-the-counter stimulants), need for detoxification from alcohol or benzodiazepines, past 300-day exposure to extended-release buprenorphine, certain chronic illnesses (especially seizures), unstable medical conditions, or presence of cardiac pacemaker.

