

(1) Meet DSM-5 criteria for opioid use disorder (any severity level) alone or comorbid with stable medical diseases (except for certain medications below)

(2) Stated desire to be opioid abstinent without medication for opioid use disorder

(3) Initiating opioid discontinuation at study site

(4) In good general health as evidenced by medical history

(5) Male or female, aged 18-65 years

(6) Provision of signed and dated informed consent and HIPAA authorization form

(7) Stated willingness to comply with all study procedures and availability for the duration of the study (including inpatient stay and participation in video assessments and remote drug screens for the duration of the 12-week outpatient study period)

(8) Use of highly effective contraception for at least 1 month prior to screening and agreement to use such a method for the duration of the study

(9) treatment will not commence until the Clinical Opiate Withdrawal Scale total score is 13 or greater (at least moderate withdrawal); thus, a consented participant could be dis-enrolled

	

(1) Acute/unstable illness: conditions making it unsafe to participate

(2) Chronic illnesses: primarily seizures and dementing illnesses, including medications for these neurological conditions

(3) Current serious psychiatric disease: psychosis, bipolar disorder

(4) Current requirement to detoxify for alcohol or benzodiazepines

(5) Current use of anxiolytics, hypnotics (prescription and over-the-counter), antidepressants, anticonvulsants, sedating H1 antihistamines (non-sedating second generation H4 antihistamines are allowed), prescription and over-the-counter stimulants

(6) Current diagnosis other than opioid use disorder requiring chronic opioid treatment

(7) Presence of a cardiac pacemaker

(8) Pregnancy or lactation. Females who do not agree to sexual abstinence or are heterosexually active and not using (self-report) medically approved birth control measures (sterilization, tubal ligation, oral/depot contraceptives, abstinence, intrauterine device, barrier method such as condom/foam, or a cervical cap combined with a spermicide), are not eligible

(9) Receiving extended-release buprenorphine within 300 days of enrollment

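### Device safety is not established after stroke, brain tumor or brain injury, but no eligibility criterion names these conditions, so a stable history can qualify

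*Combined protocol and SAP*

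**What the plan says.** The NET Device description (Safety paragraph) classes the device as Non-Significant Risk and then lists six groups in whom its safety has not been established. Group (3) is people who "have suffered a stroke, brain tumor, or brain injury". Group (2) is people who "have serious heart conditions or a cardiac pacemaker".

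Eligibility is set out in the Participant selection criteria section and in Table 2. The section's medical exclusions end with "certain chronic illnesses (especially seizures), unstable medical conditions, or presence of cardiac pacemaker". It also excludes "use of neuropsychiatric medications that may overlap with" the way the device is thought to act. In Table 2 the relevant lines are:

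- Inclusion 1: opioid use disorder, "alone or comorbid with stable medical diseases (except for certain medications below").
- Inclusion 4: "In good general health as evidenced by medical history".
- Exclusion 1: "Acute/unstable illness: conditions making it unsafe to participate".
- Exclusion 2: "Chronic illnesses: primarily seizures and dementing illnesses, including medications for these neurological conditions".

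The Data & safety monitoring section leaves the eligibility decision to the investigator alone. Figure 3 schedules a medical and psychiatric history and a physical examination at intake.

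**The concern.** The plan singles out a population in whom it says safety is unknown, then writes entry criteria that do not mention that population. The device applies current to the head through electrodes on both mastoids and is available almost continuously for up to 7 days. The Safety paragraph refers to people who have had these conditions, so it covers past events as well as active disease. If the criteria do not catch past events, whether such a person enters depends on how the investigator reads several general clauses, and two similar applicants could be treated differently. What is at stake is participant safety and consistent screening, not the analysis.

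**Working it through.** The plan states no figure to reproduce. The check is a comparison of the Safety paragraph with the criteria.

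**Step 1. The six Safety groups against Table 2.**

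| Safety group | Named in Table 2? | Where |
|---|---|---|
| (1) pregnancy, breastfeeding, under 18 | in full | exclusion 8, inclusion 5 |
| (2) serious heart condition, pacemaker | in part: pacemaker only | exclusion 7 |
| (3) stroke, brain tumor, brain injury | not at all | none |
| (4) current epilepsy | in full, as seizures | exclusion 2 |
| (5) serious psychotic illness | in full | exclusion 3 |
| (6) neurotransmitter blockers and similar | in part: listed drug classes | exclusion 5 |

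Count: 3 in full + 2 in part + 1 not at all = 6. The Participant selection criteria section does not name the three conditions of group (3) either.

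**Step 2. Do the general clauses catch a stable history?** Take an old stroke, a past brain injury and a treated brain tumor, each now stable.

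- Exclusion 1 is directed at acute or unstable illness. A stable past event is neither. The words about unsafe conditions could be stretched to reach it, but only by judgement.
- Exclusion 2 is open-ended (*primarily*), and its two examples are neurological. An investigator could place a prior stroke or tumor under it. A past event without lasting effects is not plainly a chronic illness, and nothing says it must be treated as one.
- Inclusion 4 asks for good general health by history. A person can meet this years after a stroke or injury.
- Inclusion 1 points the other way, since it admits stable comorbid disease.
- Indirect capture: those with seizures, dementia, anticonvulsant use or an unstable condition are excluded on those grounds. The gap is limited to the rest.

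So the clauses permit exclusion and none requires it.

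**Step 3. Do later rules close the gap?** Withdrawal reasons (2) and (4) in the Participant withdrawal section act after entry and do not screen. Reason (4) depends on meeting an exclusion criterion, and for these conditions no explicit one exists. Reason (2) concerns a condition or situation that arises, which fits a past event poorly.

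**Step 4. Size.** Allocation is 1:1 with 50 per arm, so the expected share of any such entrants who receive active stimulation is 50 / (50 + 50) = 0.5. The documents give no prevalence of these histories, so the number of entrants cannot be estimated.

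**The case against.** The strongest reply is that this is a gap in explicitness, not an open door. The exclusion lists are open and neurological in character, the investigator has the history and examination from intake, and the Safety paragraph is in the same document. A careful investigator would probably exclude most such people. Exposure is also mitigated: intensity is self-controlled from 0 mA, use may stop at any time, and device operation and withdrawal severity are reviewed daily. All of this stands and keeps the point modest. It does not remove it, because an exclusion that is allowed but not required can be applied unevenly.

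A reader might go further in five ways that the documents do not support.

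- *The reviewer has no guidance.* The Safety paragraph names the group, and the general clauses give grounds to act on it.
- *Eligibility review is cursory because it is rapid and remote.* The text says intake assessments are aligned with the facility's standard of care so that forms can be reviewed quickly. That describes data flow, not a superficial medical check.
- *These people are contraindicated.* Safety not being established is a weaker statement, and the paragraph does not say that everyone listed must be excluded.
- *Serious heart conditions are an equal gap.* Pacemaker is named, and the clauses on general health and unsafe conditions probably cover serious heart disease.
- *The omission shows carelessness or intent.* The medication exclusion is given a reason based on mechanism, so Table 2 need not have been built from the Safety list. No inference about motive is warranted.

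**Conclusion.** The mismatch is real. Group (3) is the only one of the six with no named item in the criteria, and a person with a stable past stroke, brain injury or treated tumor can be enrolled as the criteria stand. About one in two such entrants would be allocated to active stimulation, for up to 7 days. How many there would be is unknown and is not assumed here. The conclusion rests on the ordinary meaning of *acute*, *unstable* and *chronic* in Table 2, and on the criteria being complete as published. No effect on power, sample size or the efficacy result is claimed. It is a cheap improvement in patient safety.

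**What to change.** Add one exclusion to Table 2, and the same words to the Participant selection criteria section: *history of stroke, brain tumor, or brain injury*. Define brain injury in the protocol before the criterion is used, for example as moderate or severe traumatic injury or anoxic injury, and state how mild injury is handled. Without a definition, part of the judgement problem remains. Check the criterion against the medical history already taken at intake; no new assessment is needed. A heart-condition exclusion is not part of this change.

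If enrollment has begun, apply the exclusion to new participants only. For anyone with such a history who is still using the device, the investigator decides whether to stop it. That person stays in outpatient follow-up and in the ITT and safety sets, and is neither withdrawn nor replaced. The amendment should say this expressly, for two reasons. A newly added exclusion would otherwise allow withdrawal under reason (4), and the plan replaces withdrawn participants. If follow-up then stopped, the missing weeks would be imputed as not abstinent. The plan also treats stopping before the first hour is complete as study withdrawal, so the amendment should cover that case too.

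The cost is one amendment, some more screen failures and slightly narrower generalizability. The documents do not allow the size to be estimated. The Missing data section gives 105 expected consents and a projected 125 to cover unforeseen events, but does not say that 125 is a ceiling on consents, so the difference cannot be read as room for screen failures. If the sponsor prefers to admit these people, the protocol should say so and give the reason.

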### ***Study design***

This ITT, randomized, single-site trial uses a superiority design that compares active treatment to sham control. This trial will evaluate efficacy and safety endpoints during opioid discontinuation within an inpatient setting, and subsequent outpatient assessment of opioid and non-opioid substance use following discharge (primary and secondary endpoints, respectively). Fifty participants will be randomized to each of the two treatment arms (active and sham) and prospectively followed. **Figure 2** illustrates the study schema. **Figure 3** illustrates the schedule of activities.

As the platform for this trial, all participants receive treatment as usual (TAU), except MOUD, which they choose (as part of informed consent) not to receive as a condition of inclusion in this study. Participants could experience clinical deterioration during inpatient discontinuation of illicit opioids, prescribed opioid agonist medications (buprenorphine, methadone), and other illicit substances. Participants are instructed that device use (active or sham treatment) is self-administered, they may discontinue device use at any time and for any reason and can receive TAU for their clinical condition including MOUD and comfort medications.

The rationale for the minimum 1-hour device treatment period is to ensure a controlled degree of exposure to the device (active or sham) for all participants; based on prior open-label studies, the active device produces benefits in about 15-20 min. Completing this 1-hr period triggers study follow-up assessments. The rationale for the 7-day maximum device treatment period is to limit variability in the duration of exposure (to be treated as a covariate in analyses); as **Figure 1** indicates, the majority of participants stop active device use after about 7 days.

### ***Randomization and blinding***

The biostatistician block-randomizes assignment of the ITT population to treatment (sham vs. active) using a 1:1 allocation ratio and, within each treatment group, stratification by sex (male/female) and non-opioid substance use disorder (presence/absence). The master codebook for randomization is kept in a secure location at Wayne State University and only the biostatistician and a research assistant (backup person) can access it.

Sham treatment, which controls for placebo effects, is designed to minimize sham recognition by the sponsor, principal investigator, participants, research assistants and treatment staff (i.e. quintuple blinding). Participants in the active arm receive standard NET treatment. Participants in the sham arm receive the same standard NET treatment as the active arm but will receive no electrical stimulation (cable is disabled beforehand). Sham credibility is evaluated for both arms based on surveys following the 1-hr treatment phase, and daily during device use. A single ‘treatment perception’ question asks: “How confident are you that you are receiving the real device treatment and not the placebo (sham) treatment?” Three ‘device satisfaction’ questions ask: (1) “How satisfied are you with the NET Device?” (2) “How willing are you to use the NET Model 901 Device?” and (3) “How willing are you to recommend the NET Model 901 Device to other people undergoing opioid discontinuation?”

Active and sham arms will receive identical device care and use instructions, identical equipment, attachment methods and locations, and identical daily reviews of device operation, electrode attachment, and withdrawal severity. The treatment apparatus presents both active- and sham-assigned participants with visual cues from the device’s “heartbeat” indicator (a blinking green light-emitting diode which indicates the device is active) during treatment. Research staff instruct each participant that the equipment is designed to be self-administered, that s/he can set the level of stimulation wherever it is comfortable, that stimulation is not always (and does not need to be) sensate, and that device use may be discontinued when s/he feels it is providing no benefit.

The sham and active interventions both use the NET Device without alteration. The sham intervention uses lead wires that have been rendered non-conductive beforehand, preventing any electrical stimulation from being delivered to the participant. Before study initiation, the biostatistician allocated a random and unique Study Device Number (SDN) to each identical-looking active and sham lead wire, applying pre-printed SDN heat shrink. At the study site, the research assistant is notified electronically of participant inclusion, and selects a device and lead wires by SDN from a pre-printed randomization table for delivery of active or sham treatment. At the end of the study, all lead wires will be delivered to the biostatistician for verification against the group assignment by measuring conductivity using the sponsor-supplied validation circuit.

### ***Outcome measures***

During the 12-week outpatient period, participants will be interviewed for safety and efficacy endpoints and undergo a remote drug screen. Remote interviews reduce risk of COVID-19 exposure for the participant and research assistant, and decrease transportation barriers (increased feasibility). Each week, the research assistant hosts a live video call with the participant, and conducts a timeline follow-back (TLFB) review of opioid, MOUD, stimulant, sedative, cannabis and alcohol use for each of the prior 7 days. At discharge from the inpatient facility, each participant will be given 12 kits (plus

one spare) of the Premier Biotech OralTox OT-80605, an FDA 510(K) cleared 6-panel rapid oral fluid drug screen. Each test covers amphetamines and methamphetamine (positive cutoffs = 50 ng/ml), opioids and THC (positive cutoffs = 40 ng/ml), oxycodone and cocaine (positive cutoffs = 20 ng/ml). Each individually packaged test is sealed in foil and is marked with a lot number and expiration date. Each individual test contains a QR code that encodes a unique identification number that will be used to validate authenticity and uniqueness of the screen. The participant receives printed and verbal instructions for use from the research assistant, is observed during each test, and test results with authenticating QR code are captured as an image file by the research assistant and saved for validation. In order to conduct this FDA-qualifying study during the COVID-19 pandemic, remote test methods were evaluated for use during the outpatient phase. When this study began, FDA had only approved a limited selection of oral fluid rapid tests for use in research. The authors selected TLFB self-report as the primary source for data, supplemented by such relevant oral fluid tests as were FDA approved.

The primary efficacy endpoint is each participant's overall percentage of weekly abstinence from illicit opioid use without use of MOUD. This is defined as the percentage of each participant's negative oral fluid samples and self-reports of illicit opioid, methadone, buprenorphine, and naltrexone use per week throughout the 12-week outpatient study period. The rationale for choosing this endpoint is to perform a rigorous test of the isolated efficacy of NET, with the safety net of allowing (and measuring) participants' use of MOUDs.

During a given week, oral fluid samples and self/pharmacy reports that both indicate no illicit opioid, methadone, buprenorphine, or naltrexone use will be considered "opioid-abstinence without MOUD". Cumulative distribution function, time (days) to first use of illicit opioids, time (days) to first use of MOUD, and duration (weeks) of continuous abstinence without MOUD will be evaluated as supportive outcomes. Response profiles for each treatment arm are based on each participant's individual rates of weekly illicit opioid or MOUD use, including negative oral fluid results and daily

self (TLFB) of illicit opioid or MOUD use/non-use. **Table 1** presents explanatory cases of the primary efficacy endpoint measurement. The null hypothesis is that “opioid abstinence without MOUD” will not significantly differ between active and sham groups, whereas the alternative hypothesis is that “opioid abstinence without MOUD” will be superior in the active (relative to sham) treatment arm.

The secondary efficacy endpoint is each participant’s percentage of non-opioid drug-free weeks during the 12-week outpatient period. Non-opioids assessed include cocaine, sedatives, and stimulants. Use of alcohol and cannabis will be measured, but are not included in the secondary efficacy analysis, due to their legal status. Response profiles for each arm are based on each participant’s individual rates of weekly abstinence data, including negative oral fluid results and daily self-reports of non-opioid drug use/non-use (TLFB).

The secondary safety endpoint is the prevalence of all adverse events (AEs), serious adverse events (SAEs), adverse device effects (ADEs), serious adverse device effects (SADEs), unanticipated adverse device effects (UADEs), and device deficiencies.

Supportive and exploratory measures. Treatment retention will be measured throughout the inpatient and outpatient phases. Self-stimulation intensity (in 5-min bins), duration, and device on/off data from each NET Device are automatically transmitted to a computer server and processed offline. Opioid withdrawal symptoms, craving severity, and positive/negative affect are measured daily during the first inpatient week. Measures of depression, anxiety and stress, sleepiness, and health-related quality of life are obtained at the conclusion of inpatient and outpatient phases.

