## ***Statistical analysis plan***

Sample size determination. Sample size is based on statistical power analyses for the primary hypothesis based on single primary outcome (opioid abstinence without MOUD). A conservative approach was used to preserve power with a smaller effect size than observed from prior uncontrolled, non-blinded intervention studies with the NET Device. Power analyses examined sample sizes required to detect clinically meaningful group differences between sham and active groups. This represents standardized difference between the two groups after adjusting for the effect of the covariate “duration of inpatient residence” (which is capped at 28 days). Sample size determination was carried out *via* simulation in R-software; 5000 iterations were run in which group means were generated using a mixed-effect additive model. Sample size is a function of hypothesized effect size (standardized group difference) and the sign and magnitude of the regression coefficient (duration of inpatient residence). With projected N=100 (enrolled) there will be sufficient power to detect a standardized effect size of 0.45 or higher.

Missing data. In this ITT design, a participant is “included” (becomes part of the evaluable ITT data set) when he/she completes 1-hr of device use. We expect only 5% attrition, i.e. for 100 participants who complete 1-hr of device use, we expect to consent 105 individuals. A comparable trial of a

percutaneous electrical stimulation device for treating opioid withdrawal symptoms found that 71 of 73 enrolled participants completed 1-hr of device use, only 2.8% attrition [18]. **Table 1** explains how missing data are handled, i.e. for the primary efficacy endpoint, missing data are imputed as “not opioid abstinent without MOUD”. The definition of the primary endpoint (“opioid abstinence without MOUD”) and secondary endpoint (“non-opioid abstinence”) thus covers any intermittent missing values and loss to follow-up, and is not expected to impact power of the primary analysis. Premature study termination (e.g., death, relocation, or adverse events) may result in missing data, although this attrition is expected to be low. The projected sample size (N=125) was increased to cover unforeseen events.

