**Figure 3. Schedule of Activities**

Schedule of Activities (SoA)	Pre-Screening	Screening	Inpatient					Outpatient	
			Week -1	Week 1			Weeks 2-3	Week 4	Weeks 5-15 Week 16
Inpatient Study Day(s)		Day 1	Day 1, Baseline	Day 1, One Hour Elapsed	Days 2-7	Day 14 Day 21	Day 28 (Discharge from Site)		
Outpatient Test Weeks								OP Wk 1-11 each Day 7	OP Wk 12 Day 7
Study Site Admission		X							
Study Site Discharge							X		
End of Study									X
Informed Consent	X	X 							
Demographics		X							
Medical and Psychiatric History		MIA 							
Drug Use History		MIA 							
Physical Exam (including height and weight)		MIA 							
Vital Signs (BP, HR, RR, O2)		MIA 							
Drug Screen		MIA 					X	X	X
Contraception, Pregnancy Test, Menstrual Cycle	X						X	X	X
Drug Use Timeline Followback Interview (TLFB)								X	X
Eligibility (Inclusion/Exclusion)	X								
Contact Data	X						X		
Randomization and Stratification	X								
COWS			X 	X	X				
Administer Active/Sham Treatment (self-administration [sa])			X	sa	sa				
Opioid Craving Scale (OCS)			X	X	X	X	X	X	X
Treatment Perception (while device in use [sa])				X	sa				
Device Satisfaction Scale (while device in use [sa])				X	sa				
Device Tolerability (while device in use [sa])				X	sa				
Dass21: Depression, Anxiety and Stress			X				X		X
PANAS-SF: Positive and Negative Affect Scale (Short Form)			X	X	X				
Epworth Sleepiness Scale			X				X		X
Concomitant Medications				X	X	X	X	X	X
Adverse Events			X	X	X	X	X	X	X
Device Deficiencies				X	sa				
SF-12 Health Related Quality of Life (Short Form)							X		X

This drug screen is wider ranging to collect stratification information

Must be >13 for inclusion on Day 1

Paper (non-electronic) source data

"MIA" is Study Site Medical Intake Assessment

Notes: "OP", outpatient. "Wk", week. "sa", self-administered. "BP", blood pressure. "COWS", Clinical Opiate Withdrawal Scale, "HR", heart rate. "RR", respiration rate. "O2", oxygen saturation.

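### Each TLFB interview looks back only 7 days with no catch-up, so days before a late call or in a missed week are never asked about

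*Combined protocol and SAP*

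**What the plan says.** Under Outcome measures, the weekly video call "conducts a timeline follow-back (TLFB) review of opioid, MOUD, stimulant, sedative, cannabis and alcohol use for each of the prior 7 days". The same section makes TLFB the main data source, with oral fluid tests as a supplement. The primary endpoint is scored "per week throughout the 12-week outpatient study period". Supportive outcomes include "time (days) to first use of illicit opioids" and the matching time to first MOUD use.

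Figure 3 places the calls at "OP Wk 1-11 each Day 7", with a last one on Day 7 of week 12. TLFB is marked only in the outpatient columns.

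The Missing data paragraph of the Statistical analysis plan anticipates intermittent gaps. For the primary endpoint it counts a missing week as not abstinent, and it says the secondary endpoint's definition also handles missing values. Table 1 keeps the denominator at 12 and includes a case with a gap followed by scored weeks. The lost-to-follow-up definition applies only to someone who attends none of the post-discharge video assessments, so a person who misses some calls and returns stays in follow-up.

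The documents state no permitted window around Day 7, no recall beyond 7 days after a late or missed call, no rule assigning reported days to outpatient weeks, and no missing-day or censoring rule for the two time-to-first-use outcomes.

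**The concern.** A 7-day look-back covers the whole follow-up only if every call falls on Day 7 and none is missed. The plan does not expect that. Two consequences differ in kind.

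- **Missed call.** The next interview, as written, asks nothing about the missed week. The weekly scoring rule gives that week a value but not a date, and the time-to-first-use outcomes need dated events.
- **Late call.** The week is not missing: it has an interview and can have a sample. The missing-data rule therefore does not apply, and the week can be scored abstinent although its first days were not asked about. This reaches the primary endpoint.

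The other sources are partial. The oral fluid panel described under Outcome measures names no methadone, buprenorphine, naltrexone or sedative, and no detection window is given for the substances it does name.

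**Working it through.** **Inputs.** Look-back of 7 days and 12 outpatient weeks, so 12 × 7 = 84 days (Outcome measures); calls on Day 7 of each week (Figure 3); missing week scored 0 over a denominator of 12 (Missing data; Table 1).

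**1. The plan's own figures.** Counting abstinent weeks over 12 in the three Table 1 cases with missing weeks gives 6/12, 4/12 and 2/12, as stated. This confirms that a missed week counts against the participant. (Some Table 1 sequences look shortened by text extraction; nothing is inferred from that.)

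**2. Coverage.** A call on day c covers days c − 6 to c. Uncovered days are those of days 1 to 84 that fall in no window.

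| Call pattern | Days not asked about |
|---|---|
| All on time | 0 |
| One call 1, 2, 3 or 6 days late, others on time | 1, 2, 3 or 6 |
| Every call late by the same k days | k in total |
| 1, 2 or 3 separate calls missed | 7, 14 or 21 |

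Example: a first call on Day 9 covers Days 3 to 9, so Days 1 and 2 are unasked. If the next call is on Day 14, it covers Days 8 to 14. Days 8 and 9 are then asked about twice, with no rule on which week they count against.

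**3. Chance that a late call hides use.** Suppose the previous call was on time (or this is the first call), so k of the week's 7 days are uncovered. Suppose also that the week has u use-days placed at random and that the oral fluid test does not detect them. The chance that all u fall on uncovered days is C(k,u)/C(7,u).

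| Days late (k) | One use-day | Two use-days |
|---|---|---|
| 1 | 1/7 = 14% | 0/21 = 0% |
| 2 | 2/7 = 29% | 1/21 = 5% |
| 3 | 3/7 = 43% | 3/21 = 14% |

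**4. Missed week and time to first use.** If first use falls on day j of a single missed week and then continues daily, the next on-time interview first picks it up on its own first day, which is 8 − j days late: 1 to 7 days. If use stops before that window opens, the event is dated to a later episode or not recorded.

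**5. With recall back to the last covered day.** In the example, the Day 9 call covers Days 1 to 9 and the Day 14 call covers Days 10 to 14: 9 + 5 = 14 days, none missed and none repeated. The same holds in every pattern above where a later call takes place.

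**The case against.** The case against is substantial.

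- **The schedule tiles exactly.** With calls on Day 7, none of the 84 days is lost. A window and catch-up instruction may sit in interview forms that are not public, and the documents do not say how often calls run late. This stands as a limit on size: how often the problem arises is unknown. It does not remove the gap in the stated method.
- **A missed call cannot turn a using week into an abstinent one.** A reader might infer that it does. The missing-data rule and Table 1 rule this out for the primary endpoint, and the plan says the secondary endpoint is covered too. This stands in full.
- **Early discharge.** Inpatient stay is a covariate "which is capped at 28 days", while Figure 3 shows discharge only at Day 28 and outpatient follow-up from study week 5. A reader might infer that someone discharged on Day 7 has 28 − 7 = 21 uncovered days. That requires calls to stay fixed to study week 5. Study design places outpatient assessment after discharge, Outcome measures hands out the test kits at discharge, and the device description gives an outcome period of up to 16 weeks (28 + 84 = 112 days). All of this fits outpatient week 1 starting at discharge, which leaves no gap. Only the anchor date is unstated.
- **Other sources exist.** Pharmacy reports and the concomitant medications collected at outpatient visits can reveal prescribed MOUD. This stands for prescribed MOUD, but not for illicit opioids or for non-prescribed methadone or buprenorphine.
- **Changing recall mid-study.** The text suggests the trial was already under way, so a change would create two recall regimes. That is a real cost if it applies.

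**Conclusion.** The concern holds in a limited form. As written, a returning participant is not asked about a missed week, which leaves 7 days per missed call unobserved for the two time-to-first-use outcomes. A call k days late after an on-time call leaves k days unasked in a week that can still count as abstinent on the primary endpoint. The 14%, 29% and 43% figures (0%, 5% and 14% with two use-days) are conditional: they assume random placement of use-days and no detection by oral fluid or another source. They apply to one late-call week, not to the trial as a whole.

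Three further inferences are not supported. Alternating on-time and 2-day-late calls would leave 6 × 2 = 12 of 84 days (14%) unasked, but that pattern is assumed; uniform 2-day lateness loses only 2 days. Late or missed calls might differ between arms, but nothing in the documents shows that they do, or in which direction. Continuous abstinence is measured in weeks, so it does not belong with the two day-level outcomes.

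**What to change.** In Outcome measures, replace the fixed look-back with this rule: each TLFB covers every day since the last day covered by a completed interview and, at the first call, every day since actual discharge. Assign each reported day to its calendar outpatient week. Use the recovered days to date first illicit opioid and first MOUD use, and to correct weeks with a late call. Keep the present rule that a missed week scores as not abstinent on the primary endpoint, so that the Table 1 scores do not change.

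Days after a participant's last completed call remain unobserved. The weekly rule already scores those weeks, but the plan should say how the time-to-first-use outcomes treat them.

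As a clarification only, state in the text and in Figure 3 that outpatient week 1 starts at actual discharge.

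The cost is a change of protocol and interview-form wording, a few more minutes on calls after a late or missed visit, and somewhat longer recall for those days. If enrolment has begun, record the date of the change so that interviews under the two recall rules can be told apart.
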